3.1.7 Exclusion Criteria

3.1.7.1 Exclusion Criteria (Part A and Part B)

Participants meeting any of the following criteria for Parts A and B at the Screening Visit (Day 0) or at Day 1, unless noted otherwise, will be excluded from the study:

1. Pregnant or breastfeeding.
2. Is acutely ill or febrile 24 hours prior to or at the Screening Visit (Day 0). Fever is defined as a body temperature $\geq 38.0^{\circ}\text{C}/100.4^{\circ}\text{F}$. Participants meeting this criterion may be rescheduled within the relevant window periods. Afebrile participants with minor illnesses can be enrolled at the discretion of the investigator.
3. Current treatment with investigational agents for prophylaxis against COVID-19.

4. Has a medical, psychiatric, or occupational condition that may pose additional risk as a result of participation, or that could interfere with safety assessments or interpretation of results according to the investigator's judgment.
5. Is a healthcare worker or a member of an emergency response team.
6. Current use of any inhaled substance (eg, tobacco or cannabis smoke, nicotine vapors).
7. History of chronic smoking (≥ 1 cigarette a day) within 1 year of the Screening Visit (Day 0).
8. History of illegal substance use or alcohol abuse within the past 2 years. This exclusion does not apply to historical cannabis use that was formerly illegal in the participant's state but is legal at the time of Screening.
9. Known history of hypertension, or systolic blood pressure > 150 mm Hg in participants in Cohort 1 (≥ 18 to < 55 years old) or systolic blood pressure > 160 mm Hg in participants in Cohort 2 (≥ 55 years old) at the Screening Visit (Day 0).
10. Known history of hypotension or systolic blood pressure < 85 mm Hg at the Screening Visit (Day 0).
11. Diabetes mellitus.
12. Diagnosis of chronic pulmonary disease (eg, chronic obstructive pulmonary disease, asthma).
13. Chronic cardiovascular disease.
14. Resides in a nursing home.
15. Grade 1 or higher toxicity on clinical safety laboratory testing at the Screening Visit (Day 0).
16. Current or previous diagnosis of immunocompromising condition, immune-mediated disease, or other immunosuppressive condition.
17. Received systemic immunosuppressants or immune-modifying drugs for > 14 days in total within 6 months prior to the Screening Visit (Day 0) (for corticosteroids ≥ 20 mg/day of prednisone equivalent). Topical tacrolimus is allowed if not used within 14 days prior to the Screening Visit (Day 0).
18. Anticipating the need for immunosuppressive treatment at any time during participation in the study.

19. Positive serology for hepatitis B virus surface antigen, hepatitis C virus antibody, or human immunodeficiency virus (HIV) type 1 or 2 antibodies identified at the Screening Visit (Day 0).
20. History of anaphylaxis, urticaria, or other significant AR requiring medical intervention after receipt of a vaccine.
21. Bleeding disorder considered a contraindication to IM injection or phlebotomy.
22. Diagnosis of malignancy within previous 10 years (excluding non-melanoma skin cancer).
23. Has received or plans to receive a licensed vaccine \leq 28 days prior to the first injection (Day 1) or plans to receive a licensed vaccine within 28 days before or after any study injection. Licensed influenza vaccines may be received more than 14 days before or after any study injection.
24. Receipt of systemic immunoglobulins or blood products within 3 months prior to the Screening Visit (Day 0) or plans for receipt during the study.
25. Has donated \geq 450 mL of blood products within 28 days prior to the Screening Visit (Day 0) or plans to donate blood products during the study.
26. Participated in an interventional clinical study, other than mRNA-1273-P301 COVE, within 28 days prior to the Screening Visit (Day 0) or plans to do so while participating in this study.
27. Is an immediate family member or household member of study personnel.

3.1.7.2 Exclusion Criteria (Part C)

Participants meeting any of the following criteria for Part C at OL-D1, unless noted otherwise, will be excluded from the study:

1. Is acutely ill or febrile 24 hours prior to or at the Screening Visit (Day 0). Fever is defined as a body temperature \geq 38.0°C/100.4°F. Participants meeting this criterion may be rescheduled within the relevant window periods. Afebrile participants with minor illnesses can be enrolled at the discretion of the investigator.
2. Current treatment with investigational agents for prophylaxis against COVID-19.
3. Has a medical, psychiatric, or occupational condition that may pose additional risk as a result of participation, or that could interfere with safety assessments or interpretation of results according to the investigator's judgment.

4. History of illegal substance use or alcohol abuse within the past 2 years. This exclusion does not apply to historical cannabis use that was formerly illegal in the participant's state but is legal at the time of Screening.
5. Known history of hypotension or systolic blood pressure < 85 mm Hg at the Screening Visit (Day 0).
6. Current or previous diagnosis of immunocompromising condition, immune-mediated disease, or other immunosuppressive condition.
7. Received systemic immunosuppressants or immune-modifying drugs for > 14 days in total within 6 months prior to the Screening Visit (Day 0) (for corticosteroids \geq 20 mg/day of prednisone equivalent). Topical tacrolimus is allowed if not used within 14 days prior to the Screening Visit (Day 0).
8. Anticipating the need for immunosuppressive treatment at any time during participation in the study.
9. History of anaphylaxis, urticaria, or other significant AR requiring medical intervention after receipt of a vaccine.
10. Bleeding disorder considered a contraindication to IM injection or phlebotomy.
11. Has received or plans to receive a licensed vaccine \leq 28 days prior to the first injection (Day 1) or plans to receive a licensed vaccine within 28 days before or after any study injection. Licensed influenza vaccines may be received more than 14 days before or after any study injection.
12. Receipt of systemic immunoglobulins or blood products within 3 months prior to the Screening Visit (Day 0) or plans for receipt during the study.
13. Has donated \geq 450 mL of blood products within 28 days prior to the Screening Visit (Day 0) or plans to donate blood products during the study.
14. Participated in an interventional clinical study, other than mRNA-1273-P301 COVE, within 28 days prior to the Screening Visit (Day 0) or plans to do so while participating in this study.
15. Is an immediate family member or household member of study personnel.
16. Is SARS-CoV-2 positive by RT-PCR (central or local testing) at baseline or at any time during the mRNA-1273-P301 COVE study regardless of the presence or absence of symptoms consistent with COVID-19.
17. Had any SAE in the mRNA-1273-P301 COVE study.

3.1.8 Screen Failures (Part A: Blinded Phase Only)

Screen failures are defined as participants who consent to participate in the study but are not subsequently randomly assigned to study intervention. A minimal set of screen failure information is required to ensure transparent reporting of screen failure participants to meet the Consolidated Standards of Reporting Trials (CONSORT) publishing requirements and to respond to queries from regulatory authorities. Minimal information includes demography, screen failure details, eligibility criteria, and any SAE. In the event an eligible participant was not enrolled as a result of a cohort being full and the participant having surpassed their 28-day screening period, the investigator may rescreen the participant for enrollment by assigning the participant a new identification number and repeating all screening procedures ([Section 3.2.4](#)).

3.1.9 Participant Restrictions During the Study

3.1.9.1 General and Dietary

Participants must not eat or drink anything hot or cold within 10 minutes before oral temperature is taken.

3.2 Withdrawal of Participants From the Study or Study Dosing

3.2.1 Participant Withdrawal From the Study

Participants can withdraw consent and discontinue from the study at any time, for any reason, without prejudice to further treatment the participant may need to receive.

If participant desires to withdraw from the study because of an AE, the investigator will try to obtain agreement to follow up with the participant until the event is considered resolved or stable and will then complete the EOS electronic case report form (eCRF).

Potential reasons for withdrawing a participant from the study include the following:

- SAE
- AE (non-SAE)
- Protocol violation (specify)
- Consent withdrawal (document reason); this includes participants who, at the Participant Decision Visit, withdraw consent from continuing in the study.
- Lost to follow-up
- Other (specify)

3.2.2 Handling Withdrawal From the Study

When a participant withdraws or is withdrawn from the study, the reason(s) for withdrawal will be recorded by the investigator on the relevant page of the eCRF. These participants will be requested to complete the EOS assessments at the study completion visit as outlined in the respective SoE for each study part.

3.2.3 Lost to Follow-up

A participant will be considered lost to follow-up if he or she repeatedly fails to return for scheduled visits without stating an intention to withdraw consent and is unable to be contacted by the study site. The following actions must be taken if a participant fails to return to the study site for a required study visit:

- The site must attempt to contact the participant and reschedule the missed visit as soon as possible, counsel the participant on the importance of maintaining the assigned visit schedule and ascertain whether the participant wishes to and/or should continue in the study.
- Before a participant is deemed lost to follow-up, the investigator or designee must make every effort to regain contact with the participant (where possible, 3 telephone calls and, if necessary, a certified letter to the participant's last known mailing address or local equivalent methods). These contact attempts (eg, dates of telephone calls and registered letters) should be documented in the participant's study source document.
- Should the participant continue to be unreachable, he/she will be considered to have withdrawn from the study.
- A participant should not be considered lost to follow-up until due diligence has been completed. Date of withdrawal/lost to follow-up should be the date of last contact with the participant where safety status of the participant was assessed (eg, study site visit, telephone call).

3.2.4 Replacements (Part A, Blinded Phase Only)

Any participant who is withdrawn, who is significantly outside the allowed injection window, or who is lost to follow-up from the study may be replaced at the Sponsor's discretion.

3.2.5 Participant Withdrawal From Study Dosing

Every reasonable attempt will be made to follow up with participants for safety throughout the entire study period, even if further injection is withheld or the participant misses one or more visits.

Unless consent is withdrawn, a participant who withdraws or is withheld from receiving the second dose of study vaccine will remain in the study and complete all scheduled visits and assessments.

The investigator, in consultation with the Sponsor's medical monitor, may withhold a participant from further injection if the participant experiences any of the following:

- Becomes pregnant
- Develops, during the course of the study, symptoms or conditions listed in the exclusion criteria ([Section 3.1.7](#))
- Experiences an AE (other than reactogenicity) after injection that is considered by the investigator to be related to investigational product ([Section 3.4.8.10](#)) and is of Grade 3 (severe) or greater severity ([Appendix 2](#))
- Experiences an AE or SAE that, in the judgment of the investigator, requires study vaccine withdrawal due to its nature, severity, or required treatment, regardless of the causal relationship to vaccine
- Experiences a clinically significant change in clinical laboratory test results, vital sign measurements, or general condition that, in the judgment of the investigator, requires vaccine withdrawal
- Experiences anaphylaxis clearly attributed to study vaccine
- Experiences generalized urticaria related to the study vaccine

The reason(s) for withdrawal from further injection will be recorded.

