3.1.2 Part B, Open-Label Interventional Phase

Part B, the Open-Label Interventional Phase of the study, is prompted by the authorization of a COVID-19 vaccine under an EUA. Transitioning the study to Part B permits all ongoing study participants to be informed of the availability and eligibility criteria of any COVID-19 vaccine made available under an EUA and the option to offer all ongoing study participants an opportunity to schedule a Participant Decision Visit to know their original treatment assignment (placebo vs. mRNA-1273 [50 µg or 100 µg] vaccine).

Part B, the Open-Label Interventional Phase of the study, provides the opportunity for study participants who previously received placebo to actively request to receive 2 doses of mRNA-1273 (100 µg) vaccine. In addition, all participants who previously received 1 or 2 injections of mRNA-1273 (50 µg or 100 µg) vaccine will be able to receive a single booster dose of mRNA-1273 (50 µg). All study participants will receive a Notification Letter summarizing the basis for a COVID-19 vaccine to receive an EUA and will be asked to schedule a Participant Decision Clinic Visit.

Figure 3: Part B, Open-Label Schema

^a All participants will proceed to Part B, Open-Label Interventional Phase; begins with the Participant Decision Visit.

^b Participants who received 2 injections of mRNA-1273 100 µg during Blinded Part A.

^c Participants who received 2 injections of mRNA-1273 50 µg during Blinded Part A.

^d Participants who received 2 injections of mRNA-1273 in Part A and decline booster injection in Part B.

^e Participants who received placebo in Part A and decline 2 injections of mRNA-1273 in Part B.

^f Participants who received 2 injections of mRNA-1273 (50 µg or 100 µg) in Part A will receive one booster injection of mRNA-1273 50 µg in Part B.

^g See [Table 10](#) for directions for Part B schedule of events based on Participant status at end of Participant Decision Visit.

At the Participant Decision Clinic Visit, all participants will:

- Be given the option to be unblinded as to their original group assignment (placebo vs. mRNA-1273 vaccine [50 µg or 100 µg]),
- Be counselled about the importance of continuing other public health measures to limit the spread of disease including social distancing, wearing a mask, and hand-washing,
- Sign a revised ICF, and
- Provide a nasopharyngeal (NP) swab for RT-PCR for SARS-CoV-2 and a blood sample for serology and immunogenicity.

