3.3.2.2 Contraindications to Subsequent Injection

Prior to receiving a second injection, participants will be reassessed to ensure that they continue to meet eligibility requirements as outlined below. For Part C, if the option to administer a second injection is exercised, prior to receiving a second injection, participants will be reassessed to ensure they continue to meet eligibility requirements as outlined below.

The following events in a participant constitute absolute contraindications to any further administration of the investigational product to that participant. If any of these events occur during the study, the participant must not receive additional doses of vaccine but will be encouraged to continue study participation for safety through 6 months following last injection ([Section 3.2.5](#)).

- Symptomatic COVID-19 at the time of a second injection. If COVID-19 is suspected on or prior to administration of a second injection, further administration of investigational product must be withheld, as applicable, until COVID-19 test results are available.
- Anaphylaxis or systemic hypersensitivity reaction following the administration of vaccine.
- Any SAE judged by investigator or Sponsor to be related to study vaccine.
- Pregnancy
- Any clinically significant medical condition that, in the opinion of the investigator, poses an additional risk to the participant if he/she continues to participate in the study.

The following events constitute contraindications to administration of study vaccine at certain points in time, and if any of these events occur at the time scheduled for injection, the participant may be injected at a later date, within the time window specified in the Schedule of Events (Section 7.1), or the participant may be withdrawn from dosing at the discretion of the investigator (Section 3.2.5):

- Acute moderate or severe infection with or without fever at the time of injection
- Fever, defined as body temperature $\geq 38.0^{\circ}\text{C}$ (100.4°F) at the time of injection

Participants with a minor illness without fever, as assessed by the investigator, can be administered investigational product. Participants with a fever of 38.0°C (100.4°F) or higher will be contacted within the time window acceptable for participation and reevaluated for eligibility.

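### Protocol Sections 3.2.5 and 3.3.2.2 conflict on whether pregnancy and anaphylaxis must stop further injection, and the Part B booster is not expressly tied to the mandatory list

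*Protocol*

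**What the plan says.** Section 3.2.5 is discretionary. Having consulted the Sponsor's medical monitor, the investigator "may withhold a participant from further injection if the participant experiences any of the following". The list that follows includes:

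- "Becomes pregnant";
- "Experiences anaphylaxis clearly attributed to study vaccine";
- an AE other than reactogenicity that is "considered by the investigator to be related to investigational product" and is of Grade 3 or greater;
- an AE or SAE that, in the investigator's judgement, "requires study vaccine withdrawal due to its nature, severity, or required treatment, regardless of the causal relationship to vaccine";
- conditions from the exclusion criteria that develop during the study.

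Section 3.3.2.2 is mandatory. It describes a set of events as absolute contraindications to any further dose and says that, if one occurs during the study, "the participant must not receive additional doses of vaccine but will be encouraged to continue study participation". The set includes pregnancy, "Anaphylaxis or systemic hypersensitivity reaction following the administration of vaccine", and any SAE that either the investigator or the Sponsor judges related to the vaccine. The sentence containing the prohibition ends with a cross-reference to Section 3.2.5.

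Section 3.3.2 sends the reader to 3.3.2.2 to determine eligibility for later injections. Section 3.1.2 says that "all participants who previously received 1 or 2 injections of mRNA-1273" will be able to have a single booster in Part B. The Synopsis has a matching sentence, and Section 3.3.2 says such participants will receive it. The Synopsis and Section 4.5 make entry to Part B conditional on the eligibility criteria.

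**The concern.** A rule for stopping vaccination should give the same answer whichever section a site opens. Here pregnancy and anaphylaxis carry two levels of obligation. For anaphylaxis the triggering event is also defined in two ways, and for SAEs the two lists use different tests and different decision-makers. The cross-reference in the mandatory section leads to the discretionary one, so following it does not settle the question.

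Participant safety is at stake first. There is a smaller reporting consequence: discontinuation of study vaccine is a tabulated outcome (protocol Section 4.6.2; Part A/B SAP Section 6.2.1), so uneven application of the rule would carry into those counts.

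Part B adds a second question. Its booster comes after one or two earlier mRNA-1273 doses, yet the text does not say expressly that the mandatory list is checked against what happened in Part A.

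**Working it through.** No sample size, power or event figure is involved, so the check is a comparison of text.

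**Step 1. The two lists side by side.**

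| Event | Section 3.2.5 | Section 3.3.2.2 | Relation |
|---|---|---|---|
| Pregnancy | Listed; withholding is optional | Listed; dosing prohibited | Same event, different obligation |
| Anaphylaxis | Listed only if clearly attributed to vaccine; optional | Listed if it follows vaccination, together with systemic hypersensitivity; prohibited | Different obligation and wider trigger |
| SAE | No entry for a related SAE as such; reached through Grade 3 or greater related AE, or investigator's judgement that withdrawal is needed whatever the cause | Any SAE judged related by investigator or Sponsor; prohibited | Overlapping, not matching |

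For SAEs the mismatch runs both ways. A related SAE below Grade 3 that the investigator does not think requires withdrawal falls under 3.3.2.2 but not under either of those 3.2.5 entries. An unrelated SAE that the investigator thinks does require withdrawal falls under 3.2.5 but not under the SAE entry of 3.3.2.2. Only 3.3.2.2 gives the Sponsor a say on relatedness.

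**Step 2. Which section governs.** Section 3.3.2 names 3.3.2.2 for later injections, and 3.3.2.2 bars any further administration. Applied together, the passages lead to the bar. Section 3.2.5 does not say that it yields to 3.3.2.2.

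**Step 3. The Part B OL-D1 injection.**

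- The reassessment sentence in 3.3.2.2 is tied to a second injection. The next sentence adds an optional second injection in Part C. The Part B booster is not named, and for someone with two Part A doses it is a third mRNA-1273 injection.
- The Part A and Part B exclusion list (Section 3.1.7.1) is timed to Screening (Day 0) or Day 1 unless noted otherwise. By contrast, the opening of the inclusion criteria (Section 3.1.6) does name OL-D1.
- No item on that exclusion list names a related SAE after a Part A dose. The Part C list (Section 3.1.7.2) excludes anyone with an SAE in the earlier Phase 3 study.
- Against this, Tables 11 and 12 schedule confirmation of the inclusion and exclusion criteria, and a pregnancy test, at OL-D1.

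The residual gap is therefore narrow. It concerns express wording at one injection visit, mainly for a related SAE in Part A.

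**The case against.** The strongest reply is that a permission to withhold is not a permission to dose. Withholding satisfies both sections, while dosing a participant on the absolute list breaches 3.3.2.2. That section covers any further administration if the event occurs during the study, and Part B is part of the same study. Entry to Part B depends on eligibility. The Part A and Part B exclusions cover pregnancy (item 1), medical conditions posing additional risk in the investigator's view (item 4), and anaphylaxis, urticaria or another significant vaccine reaction needing medical intervention (item 20). Section 3.4.4 requires a pregnancy test before each vaccination in Parts A and B.

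All of this stands, and it rules out three stronger readings that a reader might infer.

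- *Two sites could act in opposite ways and both comply, so a barred participant may properly be dosed.* The documents do not support this. It requires reading 3.2.5, or the Part B offer, in isolation.
- *The second crossover dose in Part B and a second Part C dose are exposed.* They are second injections, which the 3.3.2.2 reassessment covers; Part C is named.
- *Participants with only one mRNA-1273 dose probably had a stopping event.* Section 1.3 implies (200 − 195) + (200 − 198) = 7 such participants, but gives no reasons. Section 3.3.7 anticipates second doses missed through visit noncompliance. Nor is 7 an upper bound on those with a contraindication, since an event after the second dose would also count.

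The reply does not remove the conflict itself. The exclusion criteria do not fully cure it either, because 3.2.5 puts exclusion conditions that develop during the study on its own discretionary list.

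**Conclusion.** The conflict is real for pregnancy and anaphylaxis, in obligation for both and in trigger for anaphylaxis. For SAEs the lists overlap without matching. A reader who applies every passage reaches the bar; a site relying on 3.2.5 would treat the stop as optional. The Part B wording leaves a smaller gap at OL-D1, partly closed by the conditional entry and the scheduled checks.

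The point cannot be sized in participants, because the documents do not report how many had one of these events. It changes no estimate or sample size. It deserves correction because it concerns a safety rule and costs almost nothing to settle. The conclusion assumes only that sites act on the protocol text provided; site training or other instructions outside these documents might already resolve it. No view is taken on which rule is clinically right.

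**What to change.** Reconcile Sections 3.2.5, 3.3.2.2 and 3.1.7.1 with the Part B text in the Synopsis and Sections 3.1.2 and 3.3.2, so that:

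- each event has one stated category (mandatory or discretionary), one attribution wording and one named decision-maker;
- the text says consistently how 3.3.2.2 applies to the Part B OL-D1 injection, including events recorded in Part A;
- the timing wording of the Part A and Part B exclusions agrees with the OL-D1 check in Tables 11 and 12.

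Which category each event belongs to is for the sponsor and investigators. The cost is protocol wording in an amendment. The reconciliation itself calls for no new visit, sample or analysis.
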